5.5.9 Other significant adverse events

5.5.9.1 Adverse events of special interest

Adverse events of special interest (AESI) include the anticipated risks of treatment with study drug and events that may be related to MS comorbidities. The following safety areas are addressed by the pre-defined AESI, detailed definition is given in Appendix A:

- Effect on heart rate and rhythm AESI (including hypotension)
- Hypertension AESI
- Hepatobiliary disorders / Liver enzyme abnormality AESI
- Pulmonary AESI
- Macular edema AESI
- Infection AESI
- Herpetic infection AESI
- Skin malignancy AESI
- Non-skin malignancy AESI
- Seizure AESI

5.5.9.2 Major adverse cardiovascular events

Based on a pre-defined list of PTs belonging to relevant Standardized MedDRA Queries (SMQs), AEs are selected for the major adverse cardiovascular events (MACE) adjudication board evaluation. For each case sent for MACE adjudication, the board members individually assess whether the case is a myocardial infarction, a stroke, or another AE. For fatal cases, each member determines whether the death is considered of cardiovascular, non-cardiovascular, or undetermined cause. If not all individual assessments concur, the case is classified into the above listed categories based on a consensus meeting. For data analysis, each case is assigned to one of the following categories:

- cardiovascular death (if a death case is classified as cardiovascular)
- non-fatal myocardial infarction (if the case is classified as myocardial infarction but not as cardiovascular death)
- non-fatal stroke (if the case is classified as stroke but not as cardiovascular death)
- no MACE (if the case is classified as other AE, but not as cardiovascular death).

The onset date and treatment-emergent status of a MACE is determined by the onset date and treatment-emergent status of the corresponding AE. In case more than one AE is linked to the same MACE case, the earliest treatment-emergent AE onset date determines the MACE onset date; if none of the linked AE is considered treatment-emergent, the earliest AE onset date determines the MACE onset date. This may lead to cardiovascular death MACE with an onset date prior to the date of death.

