9.9.2.4.2 Major adverse cardiovascular events

A listing of MACE events is prepared.

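### The MACE analysis categories ignore the board's finding of undetermined cause of death, so such a case is labelled either no MACE or non-fatal infarction or stroke

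*SAP*

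**What the plan says.** SAP section 5.5.9.2 describes two judgements by the adjudication board. On the event, "the board members individually assess whether the case is a myocardial infarction, a stroke, or another AE". On the death, "For fatal cases, each member determines whether the death is considered of cardiovascular, non-cardiovascular, or undetermined cause". If the members disagree, "If not all individual assessments concur, the case is classified into the above listed categories based on a consensus meeting". The consensus step therefore uses the same classes, and undetermined cause can be the final result.

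The section then states that for data analysis "each case is assigned to one of the following categories". There are four:

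- Cardiovascular death requires a death classified as cardiovascular.
- The infarction category is "non-fatal myocardial infarction (if the case is classified as myocardial infarction but not as cardiovascular death").
- The stroke category is built in the same way.
- The last is "no MACE (if the case is classified as other AE, but not as cardiovascular death").

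The only planned MACE output is in section 9.9.2.4.2: "A listing of MACE events is prepared".

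**The concern.** The board may return three causes of death, but the analysis rule asks only whether the death was cardiovascular. The undetermined class is recorded and then not used. Two labels follow that do not describe the case: *no MACE* for a death whose cardiovascular cause was not excluded, and *non-fatal* for an infarction or stroke case in a subject who died of a cause the board could not establish.

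Effects on heart rate and rhythm are the first AESI in section 5.5.9.1, so a reader will look closely at any unexplained death. The rule also departs from how the SAP treats other uncertain safety data, which it resolves to the more cautious side:

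- missing severity is taken as severe (5.5.2.2);
- missing relationship is taken as related (5.5.2.3, 5.5.2.4);
- missing seriousness is taken as serious (5.5.4);
- an ECG finding without an evaluable pre-treatment ECG is taken as new (5.5.11.2);
- an AE with no onset date is taken as treatment-emergent (12.3).

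For a death of undetermined cause the default goes the other way, and no reason is given.

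**Working it through.** The SAP gives no figure to reproduce. The check applies the rule in 5.5.9.2 to every case the board can return.

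**Inputs, all from 5.5.9.2.** Event type has 3 levels: infarction, stroke, other AE. Outcome has 4 levels: survived, cardiovascular death, non-cardiovascular death, undetermined death. This gives 3 × 4 = 12 combinations.

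**Rule.** If the death is cardiovascular, the case is a cardiovascular death. Otherwise the event type alone decides.

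| Event | Survived | CV death | Non-CV death | Undetermined death |
|---|---|---|---|---|
| Infarction | non-fatal MI | CV death | non-fatal MI | **non-fatal MI** |
| Stroke | non-fatal stroke | CV death | non-fatal stroke | **non-fatal stroke** |
| Other AE | no MACE | CV death | no MACE | **no MACE** |

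**Result.**
- All 12 combinations receive exactly one category, so the rule is exhaustive.
- The last column is identical to the first. For analysis, a death of undetermined cause is treated exactly as if the subject had survived.
- Of the 3 undetermined combinations, 2 are labelled *non-fatal* and 1 is *no MACE*.
- With the 2 non-cardiovascular combinations for infarction and stroke, 4 fatal combinations carry a *non-fatal* label. Those 2 can be defended (see the objection).

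**Other places in the SAP.** No other section says how undetermined deaths are assigned. Section 5.5.3 takes date and primary cause of death from the Death eCRF, not from adjudication. The death listing in 9.9.2.1 is therefore not specified to carry the board's class. Section 9.9.2.4.2 does not say whether its listing shows every adjudicated case or only those assigned to a MACE category.

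**After the fix.** With a separate category for undetermined deaths, the 3 cells of the last column change and the other 9 stay as they are.

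**The case against.** Several points on the other side stand.

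- **Every case is assigned.** A reader might infer that undetermined deaths drop out of the analysis. They do not: the rule places each one, under a label that does not fit.
- **The death is not hidden.** A reader might infer that an unexplained death could go unseen. Section 9.9.2.1 lists all deaths. Section 9.9.1 shows fatal SAEs in the overview and tabulates treatment-emergent AEs with fatal outcome. Section 9.9.2.4.1 shows fatal events within each AESI.
- **No rate is affected.** A reader might work out how one case shifts a percentage per arm. The SAP plans no MACE table, rate or test, so no such figure is produced.
- **Non-cardiovascular deaths.** A reader might call *non-fatal* wrong here too. If the board finds an infarction and a non-cardiovascular death, the infarction is judged not to have caused the death, and *non-fatal* can describe the event. The documents do not show this to be an error.
- **Counting undetermined deaths as cardiovascular.** A reader might infer that this is the correction needed. It is a debatable convention, and nothing in the SAP adopts it.
- **Absence from the listing.** That a *no MACE* case is left out of the MACE listing is a natural inference, but 9.9.2.4.2 does not say so.

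It can also be said that a board charter may hold a convention for such deaths. Section 5.5.9.2 refers to none, and it fixes the analysis assignment itself.

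None of this answers the central point. For an undetermined death the board has not excluded a cardiovascular cause, and the rule gives the case the same label as a survivor's.

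**Conclusion.** The point holds within narrow limits. Section 5.5.9.2 permits a final adjudication of undetermined cause and then assigns such cases as if there had been no death, in 3 of 12 combinations. This is a stated rule that gives an unsuitable label, not a detail left for later.

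The consequence is confined to the MACE classification and listing. No estimate, test or summary table changes, and the death itself appears elsewhere. What remains is a possible conflict between outputs: a subject in the death listing whose MACE category reads *no MACE* or *non-fatal*, with no planned display specified to show the board's class.

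The conclusion assumes that the rule is programmed as written and that no separate document overrides it. It has practical effect only if at least one fatal case is selected for adjudication through the pre-defined list of preferred terms and is classified as undetermined. With 136 subjects randomized that may never occur. This is a minor correction, worth making because it is cheap.

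**What to change.** In section 5.5.9.2:

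1. Add an analysis category for death of undetermined cause, separate from cardiovascular death.
2. Restrict the two *non-fatal* categories to cases without a death adjudicated as cardiovascular or undetermined. Exclude undetermined deaths from *no MACE* as well, so that the categories stay mutually exclusive.

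In section 9.9.2.4.2, state that the MACE listing includes the new category and shows the board's classification of both the event and the cause of death. An adjudicated infarction or stroke then stays visible when the case moves to the new category.

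The cost is SAP wording and a small change to the derivation and listing. No new data are needed, because the adjudication result already holds the three causes of death.

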5.5.10 Vital signs and body weight

Blood pressure data are collected in the eCRFs for both the main database and the first dose database. Weight and height are collected in the eCRF of the main database only.

5.5.10.1 Blood pressure

Systolic (SBP) and diastolic blood pressure (DBP) are measured twice (i.e., two SBP measurements and two DBP measurements) at all assessments (except the hourly post-dose assessments after first dose on Day 1 and on study drug re-initiation). For all data analyses, for derivation of baseline, last on-treatment, Day-30 follow-up, and for flagging of high or low values, the average of the first and second measurements is considered. The average calculated in the eCRF irrespective of position of the subject (supine, standing, sitting) or arm (right, left) is used. If only one measurement is available, this is used for all further derivations and summary statistics.

Baseline is flagged and absolute and percent changes from baseline are calculated for each post-baseline value, as described in Section 5.5.1. In the same manner, pre-dose values are flagged and absolute and percent change from pre-dose are calculated for the hourly post-dose assessments after first dose on Day 1 or at re-initiation.

For by-visit and by-hour tables presenting summary statistics of quantitative vital signs results, the latest (by date/time) transmitted measurement per nominal subject-visit / time point is used in case of multiple data available at that visit or visit / time point.

Assessments meeting the following conditions are flagged in the ADaM dataset:

- SBP \leq 90 mmHg or \geq 20 mmHg decrease from baseline
- SBP \leq 90 mmHg
- \geq 20 mmHg decrease from baseline in SBP
- SBP \geq 160 mmHg or \geq 20 mmHg increase from baseline
- SBP \geq 160 mmHg
- SBP \geq 140 mmHg
- \geq 20 mmHg increase from baseline SBP
- DBP \leq 50 mmHg or \geq 15 mmHg decrease from baseline
- DBP \leq 50 mmHg
- \geq 15 mmHg decrease from baseline in DBP
- DBP \geq 100 mmHg or \geq 15 mmHg increase from baseline

- DBP \geq 100 mmHg
- DBP \geq 90 mmHg
- \geq 15 mmHg increase from baseline in DBP

For all hourly post-dose assessments after first dose on Day 1 or at re-initiation flags are set for the following conditions:

- SBP \leq 90 mmHg or \geq 20 mmHg decrease from pre-dose
- \geq 20 mmHg decrease from pre-dose in SBP
- DBP \leq 50 mmHg or \geq 15 mmHg decrease from pre-dose
- \geq 15 mmHg decrease from pre-dose in DBP.

5.5.10.2 Height and Weight

Height (cm) will only be summarized in the baseline characteristics and thus no derivations (other than treatment day of assessment) are required. Absolute and percent change from baseline is calculated for each post-baseline weight (kg) value, as described in Section 5.5.1.

5.5.10.3 Body Temperature

Collected at all visits in the Body Temperature eCRF as ‘normal’ or ‘abnormal’. No definitions and derivations (other than treatment day of assessment) necessary.

5.5.10.4 Pulse rate

Collected at unscheduled visits in the Pulse Rate eCRF as ‘normal’ or ‘abnormal’. No definitions and derivations (other than treatment day of assessment) necessary.

5.5.11 12-Lead Electrocardiogram

Only the visit, date and time information of the ECG data is collected on the eCRF for both the main database and the first dose database. ECG measurement data is collected using vendor machines from ERT (central ECG provider). Data is automatically submitted to ERT by the machine, centrally read, and transferred from ERT to Actelion.

5.5.11.1 Quantitative ECG variables

Central reader ECG data contains the following quantitative measurements and derived variables: Heart rate (HR) (bpm), PR interval (ms), QRS duration (ms), QT interval (ms), QT_{cB} (ms) and QT_{cF} (ms). Heart rate is labeled “Mean heart rate” in the data transferred, however for consistency with earlier studies and to avoid misinterpretation with values coming from Holter monitoring, the label used in the CSR is “Heart rate”. Baseline is flagged and absolute and percent changes from baseline are calculated for each post-baseline value as described in Section 5.5.1. In the same manner, pre-dose values are flagged and absolute and percent changes from pre-dose are calculated for the hourly post-dose assessments after first dose on Day 1 or at re-initiation.

For by-visit and by-hour tables presenting summary statistics of quantitative ECG results, the latest (by date-time) transmitted measurement per nominal subject-visit/timepoint is used in case of multiple data available for a visit or visit/timepoint.

All assessments meeting the following conditions are flagged in the ADaM dataset:

- Heart rate \leq 50 bpm
- Heart rate \leq 45 bpm
- Heart rate \leq 40 bpm
- PR interval $>$ 200 ms and increase of $>$ 20 ms compared to baseline assessment
- QTcF/QTcB prolongations of $>$ 500 ms
- QTcF/QTcB prolongations of $>$ 480 ms
- QTcF/QTcB prolongations of $>$ 450 ms
- QTcF/QTcB increase from baseline $>$ 30 ms
- QTcF/QTcB increase from baseline $>$ 60 ms
- QTcF/QTcB prolongations of $>$ 500 ms and increase from baseline $>$ 30 ms
- QTcF/QTcB prolongations of $>$ 500 ms and increase from baseline $>$ 60 ms
- QTcF/QTcB prolongations of $>$ 450 ms and increase from baseline $>$ 30 ms
- QTcF/QTcB prolongations of $>$ 450 ms and increase from baseline $>$ 60 ms

In addition, similar notable abnormality flags are derived in relation to the pre-dose measurements for the post-dose assessments on Day 1 and start of study drug re-initiation, and for the 3-hours post-dose measurement at Week 12 visit:

- PR interval $>$ 200 ms and increase of $>$ 20 ms compared to pre-dose assessment
- QTcF/QTcB increase from pre-dose assessment of $>$ 30 ms
- QTcF/QTcB increase from pre-dose assessment of $>$ 60 ms

For presentation of these outliers in by-visit and by-hour tables, the most extreme (i.e., lowest heart rate and highest interval) is considered in case of multiple data available at a visit or visit/timepoint.

5.5.11.2 Qualitative ECG variables

Morphological ECG findings are reported by the central reader, and mapped to CDISC standard (codelist C71150, with high level categories from codelist C71152) in the SDTM.

For analyses in tables the following categories are anticipated:

- Atrioventricular Conduction
- Axis and Voltage
- Chamber Hypertrophy or Enlargement
- Conduction
- Ectopy
- Intraventricular-Intraatrial Conduction
- Rhythm Not Otherwise Specified
- ST Segment, T wave, and U wave
- Sinus Node Rhythms and Arrhythmias
- Supraventricular Arrhythmias
- Supraventricular Tachyarrhythmias
- Ventricular Arrhythmias

Findings related to interpretation or technical issues are only included in listings.

Morphological ECG findings are flagged as “New” if not present at any pre-treatment assessment (i.e., at any ECG assessed prior to the study treatment start) or “Pre-existing” if present at any pre-treatment assessment. In case of missing or non-evaluable pre-treatment ECG assessment, it is conservatively assumed that any treatment-emergent morphological ECG finding is “New”.

5.5.12 Laboratory

Laboratory tests will be performed at Visit 1 (Screening), Visit 2 (Baseline), Visit 4 (Week 2), Visit 5 (Week 4), Visit 6 (Week 12) and every 12 weeks thereafter up to Visit 18 (EOT), and at Visit 20 (FU) and, if applicable, at all corresponding visits in the PTOP. Unscheduled laboratory tests may be performed at any time during the study (Visits U1, U2, U3, etc.).

Additional lymphocyte count measurements will be performed every 4 weeks up to Week 24.

Safety laboratory samples are centrally analyzed by Covance and the results are electronically transferred to Actelion. In exceptional cases, the protocol allows the utilization of local laboratories. Local laboratory analysis results are entered in the eCRF with some exceptions for blinding reasons (e.g., lymphocytes are not entered in the eCRF, see protocol). Quantitative results from local laboratories are not summarized (i.e., not included in summary statistics or graphical representations). Qualitative results like (marked) abnormality categorization, liver test elevation categories, etc. are derived from local laboratory data and summarized together with qualitative results derived from central laboratory data.

Safety laboratory hematology, clinical chemistry and urinalysis comprise the following parameters planned as per protocol:

Hematology: Red blood cell count, Total and differential WBC counts (basophils, eosinophils, lymphocytes, monocytes, neutrophils, band forms), Platelet count, Hemoglobin, Hematocrit.

Liver function tests and coagulation: International normalized ratio (INR), alanine aminotransferase (ALT), aspartate aminotransferase (AST), (alkaline phosphatase) AP, total bilirubin (TBIL).

Clinical chemistry (excl. liver tests): Lactate dehydrogenase, Creatinine, creatinine clearance (calculated by the central laboratory using Cockcroft-Gault), Blood Urea Nitrogen, Urate, Glucose, Total cholesterol, Triglycerides, Sodium, potassium, chloride, calcium, Total protein, albumin, C-reactive protein.

Urinalysis (dipstick provided by central laboratory): pH (5.0, 6.0, 6.5, 7.0, 7.5, 8.0, 8.5), Glucose (Negative, Trace, +, ++, +++, +++++), Proteins (Negative, Trace, +, ++, +++, +++++), Occult Blood (Negative, Trace, +, ++, +++) , Leukocytes (Negative, Trace, +, ++, +++) , Bilirubin (Negative, +, ++, +++) , Urobilinogen (3.2, 16, 33, 66, ≥131). Also, for each of those parameters it is collected whether the result is normal or abnormal, and - if abnormal - whether clinically significant (no/yes).

John Cunningham Virus (JCV) serology testing: JCV antibodies (positive/negative/indeterminate).

For the above protocol planned parameters for hematology, liver tests, and clinical chemistry, the derivations detailed in Section 5.5.12.1 will be performed.

Derivations (other than treatment day of assessment) are not performed for any other laboratory parameters, and only the raw information and treatment day of assessment are listed. This includes any laboratory parameters that were not planned to be collected per the protocol, and the following protocol planned parameters:

Hepatitis B Virus Surface Antigen, Varicella Zoster Virus IgG Antibody, HIV-1/2 Antibody, Hepatitis C Virus Antibody, M. tuberculosis IFN Gamma Response, pregnancy tests (Choriogonadotropin Beta, serum / urine).

5.5.12.1 Derivations

Numerical results are converted into both conventional and standard international (SI) units as per QS document OTH-000005 (Definition of Marked Abnormalities in Laboratory Data). Results reported as below the lower limit of quantification (LLOQ) are set to the LLOQ value. Results reported as > XX are set to XX for calculation of summary statistics. For all quantitative safety laboratory data, baseline, last on-treatment, and Day-30 follow-up assessments are flagged and absolute change from baseline and percent changes from baseline are calculated for each post-baseline value, as described in Section 5.5.1.

Flags are derived according to project specific ranges for marked laboratory abnormalities as documented in the protocol [see Appendix C]. Marked laboratory abnormalities are labeled to indicate the increasing severity of abnormally low (“LL”, “LLL”), or high values (“HH”, and “HHH”) for each of the laboratory parameter listed. For INR, the general range specified in the protocol is applied to all subjects irrespective of concomitant treatment with anticoagulants.

The following flags will be derived for alanine aminotransferase (ALT), aspartate aminotransferase (AST), total bilirubin (TBIL), and alkaline phosphatase (AP):

- ALT: $\geq 1 \times \text{ULN}^*$, $\geq 3 \times \text{ULN}$, $\geq 5 \times \text{ULN}$, $\geq 8 \times \text{ULN}$, $\geq 10 \times \text{ULN}$, $\geq 20 \times \text{ULN}$
- AST: $\geq 1 \times \text{ULN}$, $\geq 3 \times \text{ULN}$, $\geq 5 \times \text{ULN}$, $\geq 8 \times \text{ULN}$, $\geq 10 \times \text{ULN}$, $\geq 20 \times \text{ULN}$
- ALT or AST: $\geq 3 \times \text{ULN}$, $\geq 5 \times \text{ULN}$, $\geq 8 \times \text{ULN}$, $\geq 10 \times \text{ULN}$, $\geq 20 \times \text{ULN}$
- TBIL $\geq 2 \times \text{ULN}$
- ALT or AST $\geq 3 \times \text{ULN}$ and TBIL $\geq 2 \times \text{ULN}$ (at the same sample date)
- ALT or AST $\geq 3 \times \text{ULN}$ and TBIL $\geq 2 \times \text{ULN}$ + AP $< 2 \times \text{ULN}$ (at the same sample date)
- INR > 1.5 combined with ALT or AST $\geq 3 \text{ ULN}$ (at the same sample date).

* ULN = upper limit of the normal range.

5.5.13 Other safety variables

5.5.13.1 Pulmonary function tests - Spirometry

Spirometry tests to assess pulmonary function will be performed at Visit 2 (Baseline), Visit 6 (Week 12), Visit 9 (Week 48) and every 48 weeks thereafter until Visit 17 (Week 144), Visit 18 (EOT), Visit 20 (FU), and at unscheduled visits (U1, U2, etc.) if clinically indicated. If applicable, spirometry tests will also be performed at the corresponding visits in the PTOP.

Spirometry tests will be conducted at site according to the ATS/ERS guidelines [Miller 2005a, Miller 2005b]. The best (largest) forced expiratory volume in 1 second (FEV₁), forced vital capacity (FVC) and peak expiratory flow (PEF) values from the three acceptable and repeatable tests will be recorded in the eCRF as absolute volume in liters and as flow in liters/second (rounded to two decimal places). These values may come from separate maneuvers. The FEV₁/FVC ratio will be derived from the FVC and FEV₁ values recorded in the eCRF.

Prior to database lock and unblinding, spirometry data are not transferred to any member of Actelion biostatistics as these data are considered to carry a moderate risk of potential unblinding. The following parameters are collected on the eCRF at each visit:

- FVC (L),
- FEV₁ (L),
- PEF (L/s).

The following variables are derived for analysis (predicted values based on Quanjer [Quanjer 1993]):

- FEV₁/FVC (%),
- Predicted normal FEV₁[L] for male subjects = $4.30 \times \text{height (m)} - 0.029 \times \text{age (years)}$ at study enrollment - 2.49;
- Predicted normal FEV₁[L] for female subjects = $3.95 \times \text{height (m)} - 0.025 \times \text{age (years)}$ at study enrollment - 2.60;
- Predicted normal FVC[L] for male subjects = $5.76 \times \text{height (m)} - 0.026 \times \text{age (years)}$ at study enrollment - 4.34;
- Predicted normal FVC[L] for female subjects = $4.43 \times \text{height (m)} - 0.026 \times \text{age (years)}$ at study enrollment - 2.89.

For the predicted normal values derivations above, age and height collected at study screening are used; also *age* is set to 25 years if age is between 18 and 25 years and a conversion factor of 0.9 must be multiplied to the predicted normal value if subject race is other than 'White'.

- Percent of the corresponding predicted normal value is also calculated for FEV₁[L] and FVC[L] as follows:

$$\text{Percent of the predicted value (\%)} = [\text{measured value}] \times 100 / [\text{predicted normal value}].$$

Baseline is flagged and absolute and percent changes from baseline are calculated for each post-baseline value, and last on-treatment and Day-30 follow-up assessments are derived as described in Section 5.5.1.

Assessments meeting the following conditions are flagged in the ADaM dataset:

- Percent change from baseline in FEV1: $< -20\%$, $< -30\%$
- Percent change from baseline in FVC: $< -20\%$, $< -30\%$
- Absolute change from baseline in %predFEV1: $< -20\%$, $< -30\%$
- Absolute change from baseline in %predFVC: $< -20\%$, $< -30\%$
- FEV1/FVC $< 70\%$
- Absolute change from baseline in FEV1 ≤ -200 mL or percent change from baseline in FEV1 $\leq -12\%$
- Absolute change from baseline in FVC ≤ -200 mL or percent change from baseline in FVC $\leq -12\%$
- Absolute change from baseline in FEV1 > -200 mL and percent change from baseline in FEV1 $> -12\%$
- Absolute change from baseline in FVC > -200 mL and percent change from baseline in FVC $> -12\%$

